## **F. CONFIDENTIALITY**

NEP educators will keep a code key with participant names and participant ID numbers so that the surveys can be matched by participant ID number across assessment time points. They will keep this code key securely locked in a filing cabinet in their County Extension Office. NEP educators will be instructed to destroy the code key upon completion of the study. Only NEP educators will have access to their code key. The code key is attached.

Researchers will keep signed consent forms in a locked filing cabinet in the graduate student office of the [name] lab in [name]. The consent forms will be kept for three years after the conclusion of study protocol. Researchers performing data entry, data analysis, and discussion of results will not have access to private identifying information. NEP educators may collect names but will be instructed to keep study data forms free from any identifiable information.

## **G. POTENTIAL RISKS TO SUBJECTS**

Risks included in the study are no more than those encountered in everyday life.

To ensure that participants do not link their name with their identification number, NEP educators will be trained to remind participants not to write their names on any surveys. The NEP also does not collect names on the NEP Evaluation Tool used as part of usual NEP protocol, which will help maintain adherence to this study protocol.

## **H. BENEFITS TO BE GAINED BY THE INDIVIDUAL AND/OR SOCIETY**

There are no direct benefits to the study participants. The benefits to society include a better informed understanding of the effects of SNAP-Ed on dietary quality, BMI, and food insecurity. This information could have policy implications such as providing more funding for the program, informing changes to the program or improvements to the program, and extending the reach of the program.

## **I. INVESTIGATOR'S EVALUATION OF THE RISK-BENEFIT RATIO**

Since the risk to study participants is no more than that found in everyday life, and the benefits to society of the implications the study may have on policy and funding, the investigators conclude that the benefits far outweigh the risks.

## **J. WRITTEN INFORMED CONSENT FORM *(to be attached to the Application Narrative)***

Written informed consent form is attached if signed consent is required by the IRB. Researchers request a waiver of signed consent.

## **K. WAIVER OF INFORMED CONSENT OR SIGNED CONSENT**

Researchers are requesting a waiver of signed consent for individuals who prefer to complete all tasks including consent electronically; however, the individual will be present to complete the verbal consent process whether he/she signs the form or provides consent electronically. Participants will be provided the attached informed consent form after the being screened for study eligibility and before proceeding to complete the in-person survey. If participants complete the screening survey electronically through the Qualtrics application on the NEP educator's iPad, they will be required to provide informed consent by selecting the "I agree" radio button at the bottom of the informed consent form before proceeding to complete the survey. If participants complete the screening survey in paper form, then they will be provided an informed consent form that will not require a signature. All participants will be provided a copy of the informed consent form through their choice of email or a paper copy.

## **L. INTERNATIONAL RESEARCH**

N/A

## **M. SUPPORTING DOCUMENTS *(to be attached to the Application Narrative)***

- Consent Forms: 1. Signed Consent and 2. Informed Consent without signature
- Recruitment advertisement flyer
- Recruitment script

- Study reminder flyer to be emailed or physically mailed
- Instructions for height and weight measurements
- Participant Information Sheet
- Participant Code Key
- Email script and Phone call script for administering dietary recall and FFQ
- Survey instruments (Screening Survey, 18-item US Household Food Security Survey Module including characteristics questions for 3 time points, NEP medium term survey, Diet History Questionnaire II questions for past year and past month reference time periods)
- Supplemental Question (pregnancy status questions for use with paper surveys at time points 2 and 3)
- A link to the ASA24 (24-hour dietary recall) demonstration website can be viewed at <https://asa24.nci.nih.gov/demo.aspx> (Microsoft Silverlight must be installed if not already: <http://www.microsoft.com/silverlight/>).
- The official participant site link to the ASA24 can be viewed at <https://asa24.nci.nih.gov>.
- A link to the Diet History Questionnaire II (DHQ II) demonstration website can be viewed at <https://appliedresearch.cancer.gov/cgi-bin/dhq2.pl?module=2&method=1>

## SNAP-Ed Sequel Statistical Analysis Plan

**Methods:** Up to 2 repeated online 24 hour dietary recalls using the Automated Self-Assisted 24-hour Recall (ASA-24) and the Diet History Questionnaire II (DHQ II) (web-based food frequency questionnaire) developed and provided by the National Cancer Institute will be used to estimate dietary intake; the Estimated Average Requirements (EAR) for nutrients (or Adequate Intake(AI) for nutrients that do not have an EAR) will be used as a dietary reference; the Healthy Eating Index-2010 will be used to characterize diet quality using data collected from the ASA-24; the 18-item US Household Food Security Survey Module (USHFSSM) will be used to assess household food security; the Nutrition Education Program (NEP) Medium Term Survey and additional questions will be used to assess participant characteristics, nutrition and health knowledge, and nutrition and health behavior

**Characteristics:** Study participant characteristics at baseline will be compared across the intervention and control groups to test for potential confounders to test for in regression models. Characteristics of participants who withdrew from the study will also be compared to those who completed the study.

**Diet Quality:** The Healthy Eating Index-2010 scoring algorithm will be used to characterize diet quality. Instructions and sample SAS code are provided by the National Cancer Institute website at <https://epi.grants.cancer.gov/hei/>. The simple algorithm will be used in order to assign HEI scores to each individual to be able to match and compare individual participants over time using regression modeling. Change in diet quality in the intervention group compared to the control group over time is one primary outcome.

**Nutrient Intake:** Mean usual nutrient intakes and distributions will be quantified at baseline and 1-year follow-up using the National Cancer Institute Method for estimating a single dietary component and change in intake from baseline and 1-year follow-up will be assessed and compared between the intervention and control groups. The website for instructions and SAS code are <https://epi.grants.cancer.gov/diet/usualintakes/>. Bootstrap methods will be applied to the data in order to estimate variability and compare mean usual intake estimates over time. Change in usual mean nutrient intake in the intervention group compared to the control group from baseline to 1 year follow-up is another primary outcome. The EAR for each nutrient will serve as the cutoff value to determine the percent of the population within the intervention and control groups that are at risk for nutrient inadequacy. Where an EAR does not exist, the percent of the population meeting or exceeding the AI will be used to determine the proportion of the population at low risk for nutrient inadequacy. The proportion of the populations at risk or at low risk is a third primary outcome and will be compared between the intervention and control groups and compared over the long-term to assess the impact of the intervention.

**Food Security:** The impact of the intervention on change in food security in the intervention group compared to the control group from baseline to 1-year follow-up will be assessed using a mixed regression model. Food security score may be used as a covariate in regression modeling or as a secondary outcome. Food security status will be characterized using the methods described in the US Guide to Measuring Food Security and in the USHFSSM survey.

**Body Mass Index (BMI):** BMI may be used as a covariate in regression modeling or as a secondary outcome.

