All participants will complete three 30 minute surveys throughout the study. Surveys will be administered by NEP educators using the Qualtrics Offline Application on their program-provided iPads or paper surveys. The first survey will be administered upon enrollment in the study. Participants in the experimental group will take the second survey after they have completed the first 4 lessons between 4 and 10 weeks after enrollment in the study. Control participants will take the second survey after 4 to 10 weeks with no lessons. Since participants will be recruited on a rolling basis, they will take surveys at different times within a designated time

period. The third survey will be administered to both groups 1 year after the second survey. Surveys are comprised of the US Household Food Security Survey Module from the United States Department of Agriculture Economic Research Service, questions querying household and individual level characteristics, and the Indiana Food and Nutrition Program Evaluation Tool.

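### The SAP seeks covariates by comparing the arms at baseline and names no baseline-outcome term for the primary HEI change or for food security, leaving a less precise unadjusted analysis open

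*SAP*

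**What the plan says.** The relevant analysis text is all in the SAP; the protocol has no analysis section that adds to it.

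- **SAP, Characteristics.** Baseline characteristics are to be "compared across the intervention and control groups to test for potential confounders to test for in regression models". No list of variables, test or threshold is given.
- **SAP, Diet Quality.** "Change in diet quality in the intervention group compared to the control group over time is one primary outcome". The stated method is to "assign HEI scores to each individual to be able to match and compare individual participants over time using regression modeling". The terms of that regression are not listed.
- **SAP, Food Security.** Change "from baseline to 1-year follow-up will be assessed using a mixed regression model". Neither its fixed effects nor its treatment of the baseline value is stated. Also: "Food security score may be used as a covariate in regression modeling or as a secondary outcome".
- **SAP, Body Mass Index.** "BMI may be used as a covariate in regression modeling or as a secondary outcome". No time point is attached to either optional covariate.
- **Protocol, section B.** Survey, recalls, height and weight are collected at all three assessments. Allocation alternates within educator from a randomly set starting arm. "The third survey will be administered to both groups 1 year after the second survey", and that assessment looks back over 12 months.
- **Protocol, section C.** Attrition of about 40% is expected, leaving about 480 of 800.

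**The concern.** A baseline covariate earns its place by predicting the outcome, whether or not the arms happen to differ on it. Baseline HEI is the obvious candidate for follow-up HEI, but under the stated search it could be left out simply because the arms looked alike. A chance difference on an unrelated variable could put that variable in.

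At least three HEI analyses fit the present wording: a plain change score, group-by-time means with separate baseline means, and a baseline-adjusted model. They differ in precision and, if the baseline gap is not due to chance, in bias. Leaving the choice open means that power for a primary outcome is not fixed in advance, and that the choice could be made after results are seen.

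A smaller point concerns food security and BMI, which are possible covariates and also possible outcomes. The study hypothesis expects food security to improve with the programme. A follow-up value in the main diet model would therefore absorb whatever part of the effect runs through it. BMI is expected to stay steady, so the worry is slight there.

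**Working it through.** **The plan's own figure.** 800 × (1 − 0.40) = 480, as protocol section C states; that is 240 per arm if dropout is equal. No effect size, SD, power or significance level is given, so there is no power calculation to reproduce.

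**Assumptions, none from the documents.** Two-sided 5%; true 1-year effect 0.25 SD; equal SD at both times; only baseline and 1-year values used; independent observations (educator clustering ignored); baseline differences due to chance. r is the baseline to 1-year correlation and is varied.

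**Variance of the arm difference, in SD²**

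- Change score, completers only: 2 × 2(1−r)/240
- Baseline-adjusted, completers: 2 × (1−r²)/240
- Unconstrained group-by-time mixed model using all 400 baselines and 240 follow-ups per arm, missing at random: 2 × [(1−r²)/240 + (1−r)²/400]

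The ratio of the second to the first is (1+r)/2: 0.65, 0.75 and 0.85 at r = 0.3, 0.5 and 0.7.

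Example at r = 0.5: the variances are 0.00833, 0.00625 and 0.00750. The standard errors are 0.0913, 0.0791 and 0.0866, so 0.25/SE is 2.74, 3.16 and 2.89.

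**Power (noncentral t)**

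| r | Change score | Mixed, unconstrained | Baseline-adjusted | Gain over change | Gain over mixed |
|---|---|---|---|---|---|
| 0.3 | 63.7% | 70.2% | 81.7% | 18.0 | 11.5 |
| 0.5 | 78.0% | 82.2% | 88.4% | 10.4 | 6.3 |
| 0.7 | 94.2% | 95.4% | 96.9% | 2.7 | 1.6 |

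Gains are in percentage points, taken before rounding.

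**Which r is plausible.** HEI is scored per person from "Up to 2 repeated online 24 hour dietary recalls". If L is the within- to between-person variance ratio, r with two recalls cannot exceed 1/(1+L/2): 0.80, 0.67, 0.50 and 0.40 for assumed L of 0.5, 1, 2 and 3. Setting 1/(1+L/2) = 0.7 gives L = 0.86, so r of 0.7 or more needs L no larger than that. L is not in the documents.

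**If the baseline gap is not due to chance.** Take a true gap of 0.1 SD among completers and no intervention effect.

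- Gap persists: the adjusted estimate is biased by 0.1(1−r) = 0.07, 0.05 and 0.03 SD at r = 0.3, 0.5 and 0.7. False positives are 12.6%, 9.7% and 7.4%; the change score stays at 5%.
- Gap regresses to the mean: the change score is biased by the same amounts. False positives are 9.9%, 8.5% and 7.1%; the adjusted analysis stays at 5%.

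**Follow-up food security as a covariate.** The amount removed is the product of two unknown paths, programme to food security and food security to HEI: 0.1 × 0.1 = 0.01 SD, or 0.2 × 0.2 = 0.04 SD. In simulation at r = 0.5, power falls from about 89% to 86% and 78% respectively.

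**The case against.** **Baseline may already be handled.** Both outcomes are framed as change, and a mixed model can carry baseline as a response. This stands in part: the plan permits baseline adjustment and nothing rules it out. But a change score, or a model with separate baseline means, does not recover the precision of adjustment, and the SAP does not say which is meant. A reader might infer that the 18-point gain at r = 0.3 applies to any unadjusted analysis. It does not: an unconstrained mixed model that keeps dropouts' baselines gives up about 11.5 points there, and the SAP does not commit to a completers-only change score.

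**The baseline search is reasonable here.** With predictable alternation, looking for confounders makes sense, and the sentence implies a second step inside the regression where the outcome link may be examined. Both are fair. Yet the first step screens on arm differences, and no rule is given for the second. Describing the arms is sound; letting the comparison choose the covariates is the weak part.

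**Adjustment is not clearly safer.** Its advantage is precision under chance imbalance, which alternation and 40% attrition may undermine. This stands. Either analysis can be biased, depending on whether a real gap persists or regresses, and the documents do not say which to expect.

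**A change-score analysis might seem to reveal a real gap.** A reader might infer that disagreement between the two analyses is evidence of one. On the same completers, the disagreement equals (1−b) times the observed baseline difference, b being the fitted baseline slope. It rescales that difference and cannot separate chance from non-chance. With 240 per arm, a 5% test of the baseline difference has only about 19% power for a 0.1 SD gap.

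**Conclusion.** The concern holds for the primary HEI change, and by the same wording for food security. The SAP's search rule is a poor way to find covariates that add precision, and no baseline-outcome term is named. Under the stated assumptions, prespecified adjustment gains 18, 10 and 3 points of power over a completers-only change score at r = 0.3, 0.5 and 0.7. Over an unconstrained mixed model that keeps dropouts' baselines, it gains about 11.5, 6 and 1.5 points. At high r the gain nearly vanishes.

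Limits: the effect size and r are assumed. The figures do not cover the two primary outcomes based on the NCI usual-intake method. They carry over to food security only if its score is analysed as continuous under the same assumptions.

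A reader might also infer that the SAP plans to adjust for follow-up food security or BMI. It does not say so. Its only described covariate search concerns characteristics at baseline, which makes baseline values the natural reading. Follow-up values are merely not excluded, so that part is a request for clarification.

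**What to change.** - Prespecify the baseline value of the outcome in the HEI model and in the food security model, either as a covariate or through a mixed model with a common baseline mean.
- Name any other prognostic baseline covariates before outcome data are seen, and report the baseline comparison of the arms descriptively.
- State that food security and BMI enter the main diet models only at their baseline values. Put follow-up values in a separately labelled mediation analysis, which would serve the mediation aim in protocol section A.
- Report a change-score analysis as a sensitivity analysis, because allocation is predictable and attrition is expected to be high. Present it as an estimate under a different assumption about baseline gaps, and do not use disagreement with the main result as a test for a non-chance gap.

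The cost is a few SAP sentences and one extra analysis; all baseline values come from the first assessment, so no new data are needed. The price is that the main estimate would be biased if a real baseline gap persists, at the sizes shown in the working.

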## APPLICATION TO USE HUMAN RESEARCH SUBJECTS

---

9. This project will be conducted at the following location(s): (please indicate city & state)
- Purdue West Lafayette Campus
- Purdue Regional Campus (Specify): \_\_\_\_\_
- Other (Specify): Indiana Nutrition Education Program class locations throughout Indiana, these may include: Emergency food distribution centers; Supplemental Nutrition Assistance Program (SNAP) offices; Women, Infant, and Children Program (WIC) offices; participant homes
10. If this project will involve potentially vulnerable subject populations, please check all that apply.
- Minors under age 18
- Pregnant Women
- Fetus/fetal tissue
- [Prisoners Or Incarcerated Individuals](#)
- University Students (PSYC Dept. subject pool \_\_\_\_)
- Elderly Persons
- Economically/Educationally Disadvantaged Persons
- Mentally/Emotionally/Developmentally Disabled Persons
- Minority Groups and/or Non-English Speakers
- Intervention(s) that include medical or psychological treatment
11. Indicate the anticipated maximum number of subjects to be enrolled in this protocol as justified by the hypothesis and study procedures: 800 (400 for control group and 400 for experimental group)
12. This project involves the use of an **Investigational New Drug (IND)** or an **Approved Drug For An Unapproved Use**.
- YES       NO
- Drug name, IND number and company: \_\_\_\_\_
13. This project involves the use of an **Investigational Medical Device** or an **Approved Medical Device For An Unapproved Use**.
- YES       NO
- Device name, IDE number and company: \_\_\_\_\_
14. The project involves the use of [Radiation or Radioisotopes](#):
- YES       NO
15. Does this project call for: (check-mark all that apply to this study)
- Use of Voice, Video, Digital, or Image Recordings?
- Subject Compensation? Please indicate the maximum payment amount to subjects. \$100  
[Purdue's Human Subjects Payment Policy](#)      [Participant Payment Disclosure Form](#)
- VO2 Max Exercise?
- More Than Minimal Risk?
- Waiver of Informed Consent?
- Extra Costs To Subjects?
- The Use of Blood?      Total Amount of Blood \_\_\_\_\_  
Over Time Period (days) \_\_\_\_\_
- The Use of [rDNA or Biohazardous materials](#)?
- The Use of Human Tissue or Cell Lines?
- The Use of Other Fluids that Could Mask the Presence of Blood (Including Urine and Feces)?
- The Use of Protected Health Information (Obtained from Healthcare Practitioners or Institutions)?
- The Use of academic records?

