### B. SPECIFIC PROCEDURES TO BE FOLLOWED

NEP educators are considered key personnel because they will have direct contact with study participants; however, they will not have any part in data entry, analysis, or dissemination of study results. NEP educators, employees of Purdue University Extension, across Indiana will help facilitate the study. NEP educators have completed CITI training as a requirement for employment through Purdue University Extension. Before recruiting study participants, participating NEP educators will attend training sessions facilitated by the co-investigators of the study. The training sessions will include instructions on how to interact with participants; answer questions related to the study; and protocol for administering surveys, measuring height and weight, keeping participant information private, and the use of identification numbers. The study goals and hypothesis will not be shared with the NEP educators in order to keep their work with the participants as unbiased as possible.

NEP educators will recruit study participants who are interested in participating in NEP. The details of recruitment are described in Section D. A screening survey determining eligibility will be administered in addition to an explanation of consent. After completion of the screening survey and consent process, NEP educators will randomize participants into one of two groups: control or experimental. The NEP educators will be assigned a random number using Excel and then listed in order from least to greatest according to their random number. The first half of the NEP educators will assign their first recruited participants to the experimental group. After the first assignment, they will alternate assigning participants to either study group in an "every other" participant fashion. The second half of the NEP educators will assign their first recruited participants to the control group. After the first assignment, they will also alternate assigning participants to either study group in an "every other" participant fashion. The control group will wait 1 year from taking the second survey before starting NEP lessons. The experimental group will start NEP lessons immediately. Participants in the experimental group must take at least the first 4 NEP lessons within a time period of 4 to 10 weeks. The NEP SNAP-Ed curriculum includes 10 lessons, and participants may take the additional 6 lessons if desired.

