### **C. SUBJECTS TO BE INCLUDED**

**Describe:** The inclusion criteria for the study population includes: an interest in taking NEP lessons, willingness to wait 1 year to start NEP lessons, eligibility for SNAP, age of at least 18 years, not pregnant, living in a household located in Indiana, ability speak and read English, willingness to complete three 30 minute surveys at the designated time intervals, willingness to provide height and weight measurements, willingness to complete one 30 minute dietary recall and 60 minute FFQ at each assessment time point, willingness to stay in touch with NEP educators, and no previous participation in NEP lessons within the last year.

The exclusion criteria only include not meeting the inclusion criteria.

Women who are pregnant will not be able to enroll in the study; however, once recruited, participants who become pregnant during the study period will be able to continue participating in the study.

The study population may be considered vulnerable because they are a low income and low resource population that may have a lower than average level of education. Precautions will be taken to minimize potential risks to the study population.

The maximum number of participants targeted for the study is  $n=800$ ,  $n=400$  in the control group and  $n=400$  in the experimental group. Previous studies were used to calculate these estimates. Based on these “short term” studies, a 7% rate of attrition ( $n=17$  out of 236) is expected to increase to approximately 40% ( $n\approx 320$  of 800) in the proposed study due to the duration of 1 year between the post-assessment and the follow-up assessment. Based on these attrition considerations and our previous work, a sample size of  $n=800$  will be the recruitment goal (control group  $n=400$  and intervention group  $n=400$ ) with an approximate final sample size of  $n=480$  expected.

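### The primary usual-intake comparisons do not tie the baseline and 1-year estimates to the same people, although about 40% loss is expected between them

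*SAP*

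**What the plan says.** The Nutrient Intake section of the SAP states: "Mean usual nutrient intakes and distributions will be quantified at baseline and 1-year follow-up using the National Cancer Institute Method". It then names two primary outcomes built on these estimates. One is change in mean usual intake, intervention against control. The other is the proportion at risk (or at low risk) of inadequacy, compared between groups and over the long term. A bootstrap will supply the variability and the comparison of means over time. The section gives no analysis set, longitudinal model, missing-data method or resampling unit.

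Protocol section C recruits up to 800, 400 per group. It cites "a 7% rate of attrition" in short-term studies, which "is expected to increase to approximately 40" per cent here, with "an approximate final sample size of $n=480$ expected". The added loss is put down to the long final interval. Section B says: "The third survey will be administered to both groups 1 year after the second survey". Attrition is not split by group.

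The SAP's only step on dropout is descriptive: "Characteristics of participants who withdrew from the study will also be compared to those who completed the study". Nothing carries the result into an estimate.

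Other outcomes are treated differently. Diet quality uses individual scores so that participants can be matched over time, and food security has a mixed regression model. Nutrient intake has neither, although protocol section F provides for linking records by participant ID.

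**The concern.** The usual-intake method yields means and distributions for a group. An analyst can therefore produce a baseline figure from everyone with baseline recalls and a 1-year figure from everyone still present, then subtract. The SAP permits this, and it is the easiest way to carry the plan out. With about two in five participants lost, the difference then mixes change in diet with change in who is being measured. If people with better diets are likelier to stay, intake appears to improve with no change in anyone's diet.

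The effect is most direct on the over-time comparisons within each arm, which the SAP plans for both means and proportions. It reaches the comparison between arms if dropout differs by arm. Because the choice is left open, two analysts could follow the SAP and obtain different primary results, and the choice could be made after the data are seen.

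**Working it through.** **The plan's own figures.** 800 x 0.40 = 320 lost and 800 x 0.60 = 480 retained; both reproduce. Prior attrition is 17/236 = 7.2%, given as 7%. Equal loss would leave 240 of 400 per arm (an assumption).

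**Assumed inputs.** The documents give no completer-leaver gap, SD, correlation, alpha or power. I assume d from 0.1 to 0.5 SD, a baseline to 1-year correlation r of 0.3 to 0.5, and equal SDs at both times.

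**Shift within an arm.** Let p be the fraction lost, and C and L the baseline means of completers and leavers. The mean of all baseline participants is (1 - p)C + pL. If no diet changes, the 1-year mean of completers is C. The apparent change is C - [(1 - p)C + pL] = p(C - L) = p x d.

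- d = 0.1: 0.40 x 0.1 = 0.04 SD
- d = 0.3: 0.40 x 0.3 = 0.12 SD
- d = 0.5: 0.40 x 0.5 = 0.20 SD

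**Bias between arms.** This is the difference between the two arms' shifts.

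- 40% loss and the same d in both arms: 0
- 45% versus 35% loss, d = 0.3 in both: (0.45 - 0.35) x 0.3 = 0.03 SD
- 40% loss in both, d = 0.3 in one arm and 0 in the other: 0.12 - 0 = 0.12 SD

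**Scale.** With 80% power, two-sided 5% and r = 0.5 (so the change has variance 2(1 - r) = 1), 240 per arm detects 2.80 x sqrt(2/240) = 0.256 SD. At r = 0.3 it is 0.256 x sqrt(1.4) = 0.30 SD. A bias of 0.12 SD is thus 40% to 47% of the detectable difference.

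**Standard error if the bootstrap ignores persons.** Take 400 people at baseline, of whom 240 are seen at 1 year. Per arm, in SD squared:

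- pairing ignored: 1/400 + 1/240 = 0.00667
- pairing kept: 0.00667 - 2r/400 = 0.00517 (r = 0.3) or 0.00417 (r = 0.5)
- SE ratio: sqrt(0.00667/0.00517) = 1.14; sqrt(0.00667/0.00417) = 1.26

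The SE of change would be overstated by about 14% to 26%.

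**False-positive rate.** With pairing kept and r = 0.5, the SE of the between-arm contrast is sqrt(2 x 0.00417) = 0.0913. For bias b, the nominal two-sided 5% rate becomes 1 - Phi(1.96 - b/0.0913) + Phi(-1.96 - b/0.0913). This is 6.2% at b = 0.03 and 26% at b = 0.12.

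**Simulation check** (4,000 replicates, 400 per arm, 40% loss, r = 0.5, no true change). With a gap of 0.25 SD in one arm only, the all-available contrast was off by 0.10 SD, as p x d predicts. Using the same completers at both times, it was off by 0.00. With a gap of 0.25 SD in both arms, the all-available contrast was off by -0.002, which is simulation noise.

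**The case against.** The strongest reply is that the SAP never says the two time points are estimated separately, or on 800 and then 480 people. That is correct. A reader might infer it, but the text fits equally well with one model containing a time term, or with the same completers at both visits. The 800 is a recruitment maximum, and recalls may be completed after the survey online or by phone, so the number with baseline intake data is unknown. Separate bootstrapping of the time points is likewise only a possibility, since the resampling unit is not stated.

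A reader might also infer that the primary outcomes are biased whenever leavers differ from stayers. For the between-arm contrast this does not follow, because equal shifts cancel. The documents give no attrition by arm, and protocol section C makes the retention contacts the same for both groups. Differential loss is plausible, because one arm has lessons at once and the other waits a year, but it is not documented.

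Finally, a reader might apply 1/sqrt(1 - r) and claim an SE inflation of 20% to 41%. That formula needs the same fully paired people at both times, which is not the case with 400 then 240 per arm.

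These replies limit the size of the point and make it conditional. They do not remove it. The SAP still leaves the analysis set and the handling of loss open for two primary outcomes, and the over-time comparisons within arms get no protection from cancellation.

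**Conclusion.** The point holds in conditional form. The plan compares usual intake and proportions at risk across a gap in which about 40% are expected to leave, and it neither ties the two estimates to the same people nor accounts for the loss.

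If all baseline participants are compared with 1-year completers, over-time change within an arm shifts by 0.04 to 0.20 SD for d from 0.1 to 0.5. The between-arm contrast shifts by nothing under equal dropout, by 0.03 SD in the milder unequal case, and by 0.12 SD when d = 0.3 in one arm only. The last is an adverse scenario and should not be read as the expected bias. All values of d and r are assumptions. The shift in the proportions at risk depends also on where each cut-off falls in the intake distribution, which the documents do not show.

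This should be corrected before analysis.

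**What to change.** In the Nutrient Intake section of the SAP:

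- State which participants enter each estimate. Fit baseline and 1 year in one usual-intake model with arm, time, time-by-arm and a person random effect.
- Report beside it the result in people with data at both time points.
- Bootstrap within arm by resampling whole persons with all their recalls from both times.
- Add a sensitivity analysis that weights 1-year records by the inverse probability of retention, modelled by arm from baseline and second-assessment data, with weights re-estimated in each replicate. People lost before the second assessment have no data there, so model retention in two steps.
- Apply the same to the proportions at risk.

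The cost is SAP wording, extra programming and somewhat wider intervals in the weighted analysis. No new data are needed. The same-people analysis removes the change in composition, but it does not remove dropout that depends on the diet change itself, and the SAP should say so.
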